6.8.2. Pharmacodynamics and Tailoring Analyses

Biomarker data from all patients undergoing biomarker assessments will be analyzed using descriptive statistics. Biomarkers will be explored at baseline for prognostic value in efficacy or safety outcomes.

Further exploratory analyses of pharmacodynamic markers will be conducted as warranted.

6.8.3. Immunogenicity

A listing will be provided of all available immunogenicity data. Additionally, a listing of immunogenicity data from those patients with at least 1 positive ADA at any time point will be provided. The frequency of patients with at least 1 positive ADA assessment, and frequency of patients who develop ADA after a negative baseline assessment will be provided. To examine the potential relationship between immunogenicity and safety, the frequency and type of AEs of special interest may be examined by overall immunogenicity status by cohort in Phase 1b and by indication in Phase 2.

6.9. Safety Analyses

All safety summaries and analyses will be based upon the safety population that includes patients that have received at least 1 dose of study drug.

6.9.1. Extent of Exposure

All study drug information and dose level assignment will be listed for all patients on therapy.

The total number of cycles received and duration of treatment for each patient will be summarised by cohort (for example, using a napoleon plot).

The following exposure-related variables will be summarised by cohort (using dose for the Phase 1b portion and histology for the Phase 2) for each of the study drugs:

- Duration of treatment
- Number of cycles received
- Number of patients with dose adjustments
- Reasons for dose adjustments
- Dose intensity as a percentage of dose received relative to the planned dose
- Dose compliance as a percentage of dose received relative to the prescribed dose (this takes into account dose adjustments)

The detailed algorithms for the exposure variables will be described in the analysis dataset requirements (ADaM requirements).

6.9.2. Adverse Events

All patients who receive at least 1 dose of either galunisertib or nivolumab will be evaluated for safety and toxicity. The CTCAE terms (by entering the appropriate CTCAE code) and severity grades will be assigned by the investigator using CTCAE). Verbatim adverse event terms will be mapped to corresponding MedDRA lower-level term (LLT) terminology within the MedDRA dictionary.

Both the CTCAE terms and MedDRA LLT will be mapped using the MedDRA dictionary hierarchy to provide PTs and body SOC terms for each dictionary. For CTCAE terms where "Other" is indicated, the CTCAE PTs will be the same as the PTs of the MedDRA PTs created from mapping through the verbatims. All safety summaries will report the PTs created from mapping the investigator assigned CTCAE term.

Treatment-emergent AEs will be identified using the CTCAE terms by comparing which events are present at baseline and post baseline and severity grades pre-dose and post-dose for preexisting conditions. Where CTCAE term is "Other," the matching MedDRA LLT will be used to determine treatment emergent. Details algorithm to identify TEAEs will be described in the analysis dataset requirements (ADaM requirements).

A listing of all AEs by patient will be presented. This listing will include patient number, AE, event start and end dates, CTCAE grade, relationship to study drug/procedure, seriousness, and outcome. A listing of serious adverse events (SAEs) will be produced using the similar format.

An overall summary will be provided for AEs. The number and percent of evaluable patients will be summarized for each category below. The summary will provide counts for all AEs, and AEs possibly related to study treatment.

- Patients with at least 1 TEAE
- Patients with at least 1 grade 3 or 4 TEAE
- Patients with at least 1 SAE
- Patients who discontinued due to AE
- Patients who discontinued due to SAE
- Patients who died due to AE on study treatment
- Patients who died due to AE within 30 days of discontinuation from study treatment

The treatment-emergent adverse events (TEAEs) will be summarized by decreasing frequency of SOC by PT and by maximum CTCAE grade regardless of causality and related to any study drug separately. The incidence of TEAE will also be summarized by dose cohort (Phase 1b) and by histology cohort (Phase 2). Additional analyses of TEAEs may be performed as deemed appropriate.

6.9.2.1. Dose Limiting Toxicities

A dose-limiting toxicity (DLT) is defined as an AE during Cycles 1 or 2 (8 weeks) that is possibly related to either study drug and fulfils the predefined criteria described in Section 7.2.2.1 of the protocol.

All DLTs, as defined in the protocol, will be listed and summarized by dose level for all patients on therapy in the Phase 1b portion of the study. Similarly, DLT-equivalent AEs occurring during Cycles 1 and 2 in the Phase 2 portion of the study will be listed and summarized.

6.9.3. Deaths, Serious Adverse events and Other Notable Events

All deaths in this study, including the reasons for death, will be listed by dose cohort (Phase 1b) and by histology cohort (Phase 2). The reasons for death will be also summarized separately for on-therapy, within 30 days of last dose of study drug, and during the long term follow-up periods.

Serious adverse events will be summarized by PT and repeated for events deemed by the investigator to be possibly related to study medication, with consolidated summary performed if

needed. The SAEs will be summarized both up to 30 and 100 days after end of therapy. A listing of SAEs will be produced.

In addition, additional analyses may be performed for TEAEs of special interest.

6.9.4. Clinical Laboratory Evaluation

All laboratory results will be reviewed using Spotfire to assess changes over time and differences across cohorts. Key findings will be illustrated graphically using line plots over time or box plots for example.

Abnormal laboratory results will be listed for all patients on therapy.

Calculated CTCAE grade using CTCAE v4.0 (or higher) will be summarised for laboratory parameters where CTCAE grades are available by dose cohort (phase 1b) and by histology cohort (Phase 2).

6.9.5. Vital Signs and Other Physical Findings

All vital signs will be reviewed using Spotfire to assess changes over time and differences across cohorts. Key findings will be illustrated graphically using line plots over time or box plots for example.

Any significant physical examination findings and results of clinical laboratory tests will be listed.

6.9.6. Electrocardiograms and Cardiac Assessment Data

Electrocardiogram (ECG) and echocardiogram (ECHO) results will be evaluated by the investigator and abnormalities, if present, will be listed.

Changes from baseline in ECG and ECHO parameters will be calculated and summarised at each visit. The ECG and ECHO parameters will be compared over time to assess change from baseline, during treatment, and during follow-up.

Myocardial information and quantitative results including PR, QRS, QTcB (Bazett's correction), QTcF (Fridericia's correction) and RR intervals will provided in patient listings for absolute and change from baseline. In addition, summaries of outlying corrected QT intervals (QTc, QTcB and QTcF) will be provided by treatment. Outlying intervals include absolute values >450, >480, and >500 msec and change from baseline >30 and >60 msec.

Cardiotoxicity serum markers (BNP, troponin I, high-sensitivity, C-reactive protein, cystatin C) will be reviewed using Spotfire to assess changes over time and differences across cohorts. All parameters will be tabulated and summarized using tables and graphs.

In addition, the results from MRI/CT scans performed for detection of aneurysm formation of the ascending aorta and aortic arch will be summarised.

Further exploratory analyses may be conducted as warranted.

6.10. Subgroup Analyses

Exploratory subgroup analyses not described in this SAP will be performed as deemed appropriate to further our understanding of the clinical trial data.

6.11. Protocol Violations

Protocol violations will be identified based on information recorded on the investigator log. In addition, a list of data dependent protocol violations will be programmatically derived to ensure systematic check of key significant protocol violations in the following categories:

- Inclusion/exclusion criteria not met
- Study drug administration non-compliance
- Informed consent violations
- Protocol violation leading to study discontinuation

Details of significant protocol violations to be checked programmatically will be detailed in the programming requirements.

6.12. Interim Analyses

Since the Phase 1b part is a dose-finding study, data will be reviewed on a cohort-by-cohort basis during the study, until the MTD (or PAD) is determined. The purpose of these cohort-by-cohort reviews is to evaluate the safety data at each dose level and determine whether a DLT has been observed that would suggest MTD has been met or exceeded. The investigators and the Lilly study team will make the determination regarding dose escalation based upon their review of the safety and tolerability data as described in this protocol.

After all patients who are deemed evaluable for the assessment of dose levels complete a DLT evaluation period or when MTD is determined, an interim safety and PK analysis may be conducted for planning next studies.

For the Phase 2 part, if DLT-equivalent toxicities occur in 33% or more of patients within a tumour-specific cohort expansion, then investigators and the Lilly CRP will assess the nature and severity of these toxicities. No additional patients will be enrolled until this safety review is completed and a decision is made either to continue at the current dose or to deescalate the dose and define a new dose for the expansion phase. The safety review and decision will be documented in writing. Trial-level safety reviews will be conducted approximately 3 months after the first patient begins study drug on Cycle 1 Day 1, approximately 6 months after the first patient begins study drug on Cycle 1 Day 1, and approximately every 6 months thereafter. These evaluations will not be assessed by any formal statistical test; only listings and summaries will be carried out.

After enrolment has completed in a cohort (n = approximately 25) and the last enrolled patient in that cohort has completed or had the opportunity to complete 3 cycles of treatment, an interim analysis will be conducted for that particular cohort (for a total of 3 separate interim analyses to be conducted when each cohort reaches 25 patients complete at least 3 cycles of treatment). The intent of the interim analysis is to evaluate preliminary antitumour activity of galunisertib in

combination of nivolumab. These interims may be combined with the ongoing trial-level safety review. Pending review of the interim data, approximately 16 additional patients may be enrolled in that particular cohort if there are more than 4 and fewer than 9 patients who demonstrate responses (determined by ORR for the NSCLC cohort and by ORR or survival for the HCC cohort). Enrolment of the other cohort(s), if not completely enrolled, will not be stopped during the interim analysis. No independent data monitoring committee will be required for this study. The interim analysis will be conducted by an assessment committee consisting of at least 1 physician and 1 statistician.

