Substantial monotherapy clinical activity has been observed in \geq second-line NSCLC patients (n=129) treated in the completed Phase 1 multidose, dose-escalation study of nivolumab (CA209003). This study showed ORRs of 22% (squamous) to 26% (nonsquamous) at the 3-mg/kg dose, greater than the historical ORR for second-line docetaxel (approximately 8%-10%) (Fossella et al. 2000; Shepherd et al. 2000; Hanna et al. 2004) and similar to that for first-line platinum doublet chemotherapy (approximately 25%-30%) (Belani et al. 2008). In addition, the 48-week PFS rate among NSCLC patients treated at the 3 mg/kg dose was 30% (both nonsquamous and squamous). By comparison, the historical median PFS for second-line docetaxel is approximately 3 months (Fossella et al. 2000; Shepherd et al. 2000; Hanna et al. 2004) and that for first-line platinum doublet chemotherapy is approximately 4 to 5.5 months (Scagliotti et al. 2008). Among all CA209003 NSCLC patients with a response, the median duration of response was 17 months. Furthermore, the AE profile for nivolumab appears favourable versus platinum doublet chemotherapy, as haematologic toxicities are currently rare and the majority of nonhaematologic toxicities are low grade and manageable.

Hepatocellular Carcinoma

There are no data published with nivolumab in HCC. A Phase 1 dose-escalation study to investigate the safety, immunoregulatory activity, PK, and preliminary antitumour activity of nivolumab in advanced HCC in patients with or without chronic viral hepatitis (CA209040) is currently ongoing.

In a study of tremelimumab (an anti-CTLA-4 antibody) in HCC (Sangro et al. 2013), investigators reported a good safety profile; no patients needed steroids because of severe immune-mediated AEs. Some patients had a transient intense elevation of transaminases after the first dose but not following subsequent cycles. PR rate was 17.6% and disease control rate was 76.4%. TTP was 6.48 months (95% CI: 3.95–9.14). A significant drop in viral load was observed while new emerging variants of the hypervariable region 1 of hepatitis C virus (HCV). HCV replaced the predominant variants present before therapy, particularly in those patients with a more prominent drop in viral load. This antiviral effect was associated with an enhanced specific anti-HCV immune response.

Additional information may be found in the nivolumab IB, Section 5.4.

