6.2.2. Phase 2 Cohort Expansion

The purpose of the cohort expansions is to gather additional safety, PK, tolerability, preliminary efficacy and pharmacodynamic information regarding the combination of galunisertib and nivolumab 3 mg/kg. Once the safety profile of all doses tested has been characterised and the MTD or PAD of combined administration of galunisertib and nivolumab has been defined in the Phase 1b part, the Phase 2 cohort expansions will be initiated at the MTD, or PAD. Treatment doses in the cohort expansion groups will not exceed the MTD. Two expansion cohorts will be tested in order to demonstrate efficacy of the combination in NSCLC and HCC. If DLT-equivalent toxicities occur in 33% or more of patients within a tumour-specific cohort expansion in the first 2 cycles, then investigators and the Lilly CRP will assess the nature and severity of these toxicities. No additional patients will be accrued until this safety review is completed and a decision is made either to continue at the current dose or to deescalate the dose

and define a new dose for the expansion phase. The NSCLC cohort (NSCLC has demonstrated activity with nivolumab monotherapy) and the HCC cohort (HCC has documented monotherapy activity with galunisertib) will be used to assess activity of the combination. Additional cohorts could be considered after reviewing the Phase 1b dose-escalation data to further explore activity of the combination. Any additions would require an amendment.

Approximately 25 patients will be initially enrolled in each cohort. These cohorts may be expanded depending upon activity observed in each individual cohort. These patients will be enrolled to allow for a more precise estimate of the ORR in these tumour types where preliminary data or Phase 3 data have suggested activity for monotherapy. See Section 7.2.3 for dosing information. For all tumour types, patients should receive a minimum of 6 cycles of therapy since responses may take up to 4 to 6 cycles unless they meet 1 of the discontinuation criteria. Patients may continue on combination therapy past 6 cycles if in the opinion of the investigator and the Lilly physician the patient is deriving benefit.

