10.1.1. Sample Size

...

For HCC ~~and glioblastoma~~, the response is defined based on ORR or survival at 10 months. ...

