5.2. Determination of Sample Size

For the Phase 1b dose escalation, a 3+3+3 design will be used to assess the safety of galunisertib in combination with nivolumab 3 mg/kg. Between 3 and 12 additional patients may be enrolled in a cohort to achieve the minimum of 3 evaluable patients if dropouts or dose interruptions or reductions occur that result in a patient being nonevaluable for DLTs.

Although the primary objective remains safety of the combination for the Phase 2 cohort expansion part, the sample size appears to be adequate to evaluate preliminary antitumour activity of the combination.

When the 25th patient from each cohort has completed at least 3 cycles, an interim analysis will be conducted. Two-stage design criteria (Simon 1989) will be used to evaluate whether additional patients for that cohort will be enrolled. The null hypothesis that the null response

rate is 20% will be tested against a 1-sided alternative. If there are 4 or fewer responses in the initial 25 patients who have been enrolled and either discontinued from their allocated treatment or completed at least 3 cycles, no additional patients will be enrolled. If there are \geq 9 responses, then no additional patients will be enrolled into this cohort in Phase 2. If there are 5 to 8 responses, then approximately 16 additional patients may be accrued for a total of approximately 41 patients for that cohort.

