6.7.1. Endpoint Definitions

The following efficacy endpoints will be determined:

Overall response rate (ORR) is the proportion of patients who achieved a complete response (CR) or partial response (PR) as their best overall response out of all patients treated set.

Tumour responses will be assessed using the CCI guidelines for patients with NSCLC, HCC, and tumours other than glioblastoma.

Tumor responses will be assessed using the CCI guidelines for patients with glioblastoma.

Best response is determined from a sequence of responses assessed for each patient per the respective guidelines.

Disease Control Rate (DCR) is defined as the proportion of treated patients achieving a best overall response of complete response (CR), partial response (PR), or stable disease (SD) as their best overall response out of all patients treated set.

Change in tumour size (CTS) will be assessed in each patient using radiographic imaging. This endpoint will be based on tumour measurements collected by the centers according to the applicable guidelines.

- For patients with NSCLC, HCC, and tumours other than glioblastoma, tumour size is defined as the sum of the largest diameter for each target lesions at each tumour evaluation for CCI
- For patients with glioblastoma, tumor size is defined as the sum of the largest diameter for each measurable lesion at each tumor evaluation for **COLO**. Change in tumour size is defined as the percent change in tumour size from the baseline evaluation to the evaluation at the each tumour evaluation, only including the tumors present at baseline.

The change in tumour size corresponding to the best response for each patient will be represented in waterfall plots.

Time to Response is defined only for responders. It is measured from the date of first study treatment to the first documented response.

Duration of Response will be calculated for ORR and is defined only for responders. It is measured from the date of documented response to the date of first progression of disease or the date of death due to any cause, whichever is earlier. For each patient who is not known to have died or to have had a progression of disease at the cut-off date, duration of response will be censored at the date of last objective response assessment prior to the date of any subsequent systemic anticancer therapy.

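### The HCC interim applies cut-offs built on a 20% response null to response or survival, at a look too early to confirm 10-month survival in most patients unless accrual is slow

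*SAP*

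**What the plan says.** SAP 5.2 describes a two-stage rule for each cohort. The null response "rate is 20% will be tested against a 1-sided alternative". With 4 or fewer responses in the first 25 patients, or with 9 or more, no further patients are enrolled. Between those limits, "If there are 5 to 8 responses, then approximately 16 additional patients may be accrued", giving about 41 in total.

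SAP 6.12 and Protocol 10.8 state what is counted against the same limits: "determined by ORR for the NSCLC cohort and by ORR or survival for the HCC cohort". Neither passage gives a survival time point. One is visible in the amendment (c) listing of Protocol 10.1.1 (Attachment 13), in wording that was kept when the glioblastoma words were struck: for HCC, "the response is defined based on ORR or survival at 10 months".

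The look takes place once the last enrolled patient "has completed or had the opportunity to complete 3 cycles of treatment". A cycle is 28 days (Protocol 7.2.1). SAP 6.7.1 defines the overall response rate on tumour response alone: it "is the proportion of patients who achieved a complete response (CR) or partial response (PR) as their best overall response".

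**The concern.** A 20% null and cut-offs of 4 and 9 of 25 describe a tumour response rate. In HCC the visible text puts a second endpoint into the same count. Two things follow.

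- **Timing.** Survival to 10 months cannot be confirmed in a patient followed for three months, so the number of HCC patients who can qualify through survival is set by how slowly the cohort enrolled.
- **Null.** Twenty per cent is not a natural null for 10-month survival in patients with ECOG 0 or 1 and Child-Pugh A disease. Background survival alone could exceed it.

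If the two criteria are combined patient by patient, survival can only raise the count. An HCC cohort with few tumour responses could then escape the low-response stop and enter the zone where about 16 more patients may be enrolled, for reasons unrelated to drug activity. The same count would also mean different things in HCC and NSCLC.

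**Working it through.** **The plan's own figure.** 25 + 16 = 41, as stated. Alpha, power, the alternative rate and the final cut-off are not visible, so no stated operating characteristic can be reproduced.

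**Tumour response alone (exact binomial, n = 25, every response observed).**

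| True rate | P(4 or fewer) | P(5–8) | P(9 or more) |
|---|---|---|---|
| 10% | 0.902 | 0.098 | 0.000 |
| 20% | 0.421 | 0.533 | 0.047 |

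**Timing (needs no assumption).** 3 × 28 = 84 days, and 84/30.44 = 2.76 months. This is a minimum, because SAP 5.2 says at least 3 cycles. A patient can be confirmed alive at 10 months only if he or she started 10 − 2.76 = 7.24 months or more before the last patient. A death before 10 months is known whenever the patient started.

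**Null.** With exponential survival, S(10) = 0.5^(10/median). This gives 0.315, 0.420 and 0.500 at medians of 6, 8 and 10 months. It equals 0.20 only at a median of 10 × ln(0.5)/ln(0.2) = 4.3 months.

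**Effect on the count.** Accrual time and HCC survival are not in the visible text, so these inputs are assumptions:
- 25 starts evenly spaced over A months, with the look at A + 2.76 months;
- exponential survival, median 8 months;
- true response rate 10%;
- a patient alive short of 10 months counted on response only.

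The per-patient probability of counting is 1 − (1 − 0.10)(1 − 0.420) = 0.478 if 10 months of follow-up is available, and 0.10 if not. This treats response and survival as independent. The sum over 25 unequal probabilities is exact.

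| Accrual (months) | 6 | 12 | 18 | 24 |
|---|---|---|---|---|
| Patients with 10 months of follow-up | 0 | 10 | 15 | 17 |
| Expected number with known 10-month status, deaths included | 9.6 | 16.1 | 19.0 | 20.3 |
| Expected count | 2.5 | 6.3 | 8.2 | 8.9 |
| P(4 or fewer) | 0.90 | 0.18 | 0.04 | 0.02 |
| P(5–8) | 0.10 | 0.69 | 0.53 | 0.41 |
| P(9 or more) | 0.00 | 0.13 | 0.43 | 0.57 |

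For example, at A = 12 the expected count is 10 × 0.478 + 15 × 0.10 = 6.28.

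**Sensitivity.**
- If every responder also survives 10 months, the per-patient probability with full follow-up falls to 0.420, and P(4 or fewer) is 0.90, 0.28, 0.09 and 0.05.
- With 12-month accrual and medians of 6, 8 and 10 months (independent case), P(4 or fewer) is 0.34, 0.18 and 0.10.
- At accrual under 7.24 months nobody can qualify through survival, so there is no effect.

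**The case against.** The strongest objection is redaction. The part of Protocol 10.1.1 that defines HCC response is blacked out, and the power tables are not visible. A reader might infer that the plan has no HCC survival null and no rule for patients alive short of 10 months. The documents do not support that: either may stand in the hidden text and could answer part of this point. What remains is that the visible SAP 5.2 states one 20% null per cohort with no HCC exception, and that the look is defined by 3 cycles.

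A second objection is that tumour response at this look also depends on accrual. Protocol 6.2.2 says "patients should receive a minimum of 6 cycles of therapy since responses may take up to 4 to 6 cycles", and 12, 6, 4 and 3 of 25 patients would have under 6 cycles of follow-up at 6, 12, 18 and 24 months of accrual. This stands. As an illustration, suppose a third of responses appear by each of Cycles 2, 4 and 6. At a true rate of 20%, P(4 or fewer) is then 0.64, 0.53, 0.50 and 0.47, against 0.42 when all responses are observed. So it would be wrong to infer that a CR+PR count is free of accrual effects. That bias runs towards stopping an active cohort; the survival route runs towards passing an inactive one.

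Third, the consequence is limited. Expansion is optional and reviewed by a committee with a physician and a statistician. Activity is a secondary Phase 2 objective, and SAP 6.7.2 reports response rate and survival separately. The 9-or-more zone only ends enrolment; no visible text attaches a go decision to it. All of this stands, and it limits the point to the HCC expansion decision.

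Finally, the word 'or' might operate at cohort level, with survival counted separately. That would change the probabilities above, but a separate survival count would meet the same immaturity and still need its own null.

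**Conclusion.** The concern holds on the visible text. The HCC rule sets a partly immature survival endpoint against cut-offs tied to a 20% response null. The timing gap (at least 2.76 months of follow-up against 10) needs no assumption. The size does: under the assumptions listed, with a 10% response rate and 12-month accrual, the chance that the low-response stop applies falls from 0.90 to 0.18 (0.28 if all responders survive 10 months). The chance of landing in the only zone that permits about 16 more patients rises from 0.10 to 0.69. With accrual under 7.24 months neither figure moves.

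Two stronger readings should be avoided. It is not true that 10-month status is unknown for every recent starter, because early deaths are known; what is missing is confirmation of survival. Nor does this threaten the Phase 2 primary objective, which is safety. It is worth fixing before the HCC interim, with medium confidence because of the hidden text.

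**What to change.** In SAP 5.2 and 6.12 and Protocol 10.1.1 and 10.8:

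1. Apply the 20% null and the 4/9-of-25 cut-offs to CR+PR in both cohorts.
2. Keep HCC survival as a separate criterion with its own null rate and cut-offs, judged when all 25 patients have reached 10 months or died.
3. At the 3-cycle look, show the committee Kaplan-Meier survival as supporting information only.
4. If the blacked-out text already holds an HCC survival null or a rule for patients short of 10 months, align SAP 5.2 and 6.12 with it.

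Dropping survival altogether is not the request; that would be a trade-off for the sponsor.

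The cost is a protocol amendment and a SAP update, with no new data. The survival part of the HCC decision would come about 7 months later (10 − 2.76 = 7.24). A CR+PR count at 3 cycles can still miss late responders, so the committee should see how many patients have had fewer than 6 cycles of follow-up.
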